### **6.5.4 Laboratory evaluations**

In the case where a laboratory assessment that is listed in the inclusion/exclusion criteria is considered a clinically significant abnormality at screening, the assessment may be repeated once (for the purpose of inclusion), and in any case, prior to enrollment, to rule out laboratory abnormality. If the repeat value is still a clinically significant abnormality, the subject should be excluded from the study.

In the case where a laboratory range is **not specified by the protocol**, but is outside the reference range for the center at screening, a decision regarding whether the result is of clinical significance or not shall be made by the Investigator and shall be based, in part, upon the nature and degree of the observed abnormality. The assessment may be repeated once (for the purpose of inclusion) and in any case, prior to enrollment/randomization, to rule out laboratory abnormality.

In all cases, the Investigator must document in the source documents, the clinical considerations (i.e., result was/was not clinically significant and/or medically relevant) in allowing or disallowing the subject to continue in the study.

Clinically relevant deviations of laboratory test results occurring during or at completion of the study must be reported and discussed with Novartis personnel. The results should be evaluated for criteria defining an adverse event and reported as such if the criteria are met. Repeated evaluations are mandatory until normalization of the result(s) or until the change is no longer clinically relevant. In case of doubt, Novartis personnel should again be contacted.

#### **6.5.4.1 Hematology**

Hemoglobin, hematocrit, RBC, WBC count with differential (monocytes, eosinophils, basophils, neutrophils, lymphocytes) as percentage or as absolute value (depending on the standard reporting procedure of the central or local lab), and platelet count.

#### **6.5.4.2 Clinical chemistry**

Albumin, alkaline phosphatase, total bilirubin, bicarbonate/CO2, calcium, cholesterol, chloride, creatinine, CK, γ-GT, glucose, LDH, inorganic phosphorus, lipase, amylase, magnesium, potassium, total protein, AST, ALT, sodium, triglycerides, BUN and uric acid.

If the total bilirubin concentration is increased above 1.5 times the upper limit of normal, direct and indirect reacting bilirubin should be differentiated.

#### **6.5.4.3 Urinalysis**

A midstream urine sample (approximately 30 mL) will be obtained, in order to avoid contamination with epithelial cells and sediments, and allow proper assessments.

A semi-quantitative "dipstick" evaluation for the following parameters will be performed: specific gravity, pH, glucose, protein, bilirubin, ketones, leukocytes and blood.

If the dipstick result is positive for protein leucocytes and/or blood, the sample will be sent for microscopic analysis of WBC, RBC and casts.

#### **6.5.5 Electrocardiogram (ECG)**

ECGs will be collected at the pre-specified times. Standard 12-lead ECGs will be performed. Data will include the following: time of ECG, heart rate, PR interval, RR interval, QT interval (uncorrected) and QRS duration. Original ECG tracings, appropriately signed, will be archived at study site. This assessment will be evaluated by a central laboratory, but the investigator will be responsible for determining eligibility based on the ECG.

#### **6.5.6 Pregnancy**

Pregnancy tests are required of all female patients regardless of reported reproductive/menopausal status.

Serum pregnancy tests will be performed at screening; at all other times urine pregnancy tests may be used. A female patient in this study may not receive LFG316 until the screening pregnancy test is determined to be negative.

If a urine pregnancy test is performed and is found to be positive, serum -hCG will be performed. If serum -hCG is positive, the patient must be discontinued from the trial.

#### **6.5.7 Meal Record**

Not applicable.

#### **6.5.8 Chest X-ray**

Not applicable.

## 6.5.9 Ocular assessments

### 6.5.9.1 Post-injection safety assessment

Following IVT injection of LFG316, perfusion of the central retinal artery should be verified by indirect ophthalmoscopy; in case of non-perfusion, treat with anterior chamber paracentesis. Normalization of intraocular pressure should be verified within 30 minutes of the injection. Intraocular pressure should be re-measured again at 60 minutes post-injection if the pressure is elevated  $> 10$  mmHg above baseline or above 30 mmHg when measured at 30 minutes post-injection.

### 6.5.9.2 Best corrected visual acuity

ETDRS best-corrected visual acuity will be obtained in each eye separately under classified ETDRS conditions. This assessment is to be performed prior to pupil dilation. The number of letters read correctly (for each eye) will be recorded in the appropriate eCRF page.

### 6.5.9.3 Slit lamp biomicroscopy

Slit lamp exam of the adnexae, conjunctiva/sclera, cornea, anterior chamber, iris, and lens will be obtained on both eyes for each patient according to the [Assessment schedule](#). Attention should be directed to the presence of any anterior chamber cell or flare. Results from the slit lamp biomicroscopy exam (for each eye) will be recorded in the appropriate eCRF page.

### 6.5.9.4 Anterior Chamber cells assessment

Anterior chamber cell score will be evaluated by slit lamp biomicroscopy. The anterior chamber cells score will be determined according to the SUN criteria ([Jabb et al 2005](#)) as described in [Table 6-1](#).

### 6.5.9.5 Dilated ophthalmoscopy

Dilated exam of the vitreous, optic disc, retinal vessels, macula, and retinal periphery will be obtained on both eyes for each patient according to the [Assessment schedule](#). Dilated ophthalmoscopy should be performed right after LFG316 IVT injection. Immediate anterior chamber paracentesis should be performed if central retinal artery is not perfused.

### 6.5.9.6 Vitreous haze assessment

Vitreous haze will be evaluated with an indirect ophthalmoscope and a hand-held 20-diopter lens. Haze is defined as a reduction in the clarity of fundus details seen through the vitreous; the degree of haze will be quantified by the examiner comparing the view to standard NEI photographs ([Nussenblatt et al 1985](#)). The standard photographs provide a grading scale with photographs of fundi with vitreous haze grades "0" (zero), "trace" (which counts as 0.5+), 1+, 2+, 3+, and 4+. If the amount of vitreous haze appears to fall between two integer grades, the value would be recorded as halfway between the grades. For example, if the haze was intermediate between grades 1+ and 2+, the value would be recorded as 1.5+. The "trace" photographs correspond to 0.5+, so there is no intermediate value allowed between the grade 0 and trace, nor between trace and grade 1+. In this protocol, the words "step" and "grade" are used synonymously. One step or grade means a change of

one full unit except for the "trace" grade. For example, a change from grade 2+ to grade 1+ would count as an improvement of one grade (one step), as would a change from grade 2.5+ to grade 1.5+. However, a change from grade 1+ to 0 would count as two grades or two steps, since it would include the "trace" grade. A change from 1.5+ to "trace" would count as a change of one grade.

### **Color fundus photography**

Color fundus photography will be performed on the designated eye(s) for each patient according to the [Assessment schedule](#) and the imaging manual. Color fundus photos will be evaluated according to AREDS scale. Color fundus photos will be transferred according to the imaging manual provided.

## **6.6 Pharmacokinetics**

### **6.6.1 PK Blood Collection and Processing**

All blood samples will be taken by either direct venipuncture or an indwelling cannula. For a detailed sampling schedule please refer to the [Assessment schedule](#) and [Section 13-Appendix 1](#).

Corporate Confidential Information

For all participating patients, the date and exact time of each blood draw must be recorded on the PK Blood Collection page in the eCRF. Sampling problems will be noted in the Comments section of the PK Blood Collection page eCRF page.

### **6.6.2 Urine Collection and processing**

Not applicable.

### **6.6.3 Pharmacokinetic analytical method(s)**

Corporate Confidential Information

## **6.7 Other assessments**

### **6.7.1 Health-related quality of Life**

Not applicable.

Corporate Confidential Information

## Corporate Confidential Information

## **7      Safety monitoring**

### **7.1      Adverse events**

An adverse event is the appearance or worsening of any undesirable sign, symptom, or medical condition occurring after starting the study drug even if the event is not considered to be related to study drug. Study drug includes the investigational drug under evaluation and the comparator drug or placebo that is given during any phase of the study. Medical conditions/diseases present before starting study drug are only considered adverse events if they worsen after starting study drug. Abnormal laboratory values or test results constitute adverse events only if they induce clinical signs or symptoms, or are considered clinically significant, or require therapy.

The occurrence of adverse events should be sought by non-directive questioning of the subject at each visit during the study. Adverse events also may be detected when they are volunteered by the subject during or between visits or through physical examination, laboratory test, or

other assessments. All adverse events must be recorded on the Adverse Events eCRF with the following information:

1. the severity grade (mild, moderate, or severe)
2. its relationship to the study drug(s) (suspected/not suspected)
3. its duration (start and end dates or if continuing at final exam)
4. whether it constitutes a serious adverse event (SAE)

An SAE is defined as an event which:

- is fatal or life-threatening
- results in persistent or significant disability/incapacity
- constitutes a congenital anomaly/birth defect
- requires inpatient hospitalization or prolongation of existing hospitalization, unless hospitalization is for:
  - routine treatment or monitoring of the studied indication, not associated with any deterioration in condition
  - elective or pre-planned treatment for a pre-existing condition that is unrelated to the indication under study and has not worsened since the start of study drug
  - treatment on an emergency outpatient basis for an event not fulfilling any of the definitions of a SAE given above and not resulting in hospital admission
  - social reasons and respite care in the absence of any deterioration in the patient's general condition
- is medically significant, i.e., defined as an event that jeopardizes the patient or may require medical or surgical intervention to prevent one of the outcomes listed above

**Unlike routine safety assessments, SAEs are monitored continuously and have special reporting requirements; see [Section 7.2](#).**

If an adverse event involves an eye, the affected eye(s) must be specified.

All adverse events should be treated appropriately. Treatment may include one or more of the following: no action taken (i.e., further observation only); study drug dosage adjusted/temporarily interrupted; study drug permanently discontinued due to this adverse event; concomitant medication given; non-mug therapy given; patient hospitalized/patient's hospitalization prolonged. The action taken to treat the adverse event should be recorded on the Adverse Event eCRF.

Once an adverse event is detected, it should be followed until its resolution or until it is judged to be permanent, and assessment should be made at each visit (or more frequently, if necessary) of any changes in severity, the suspected relationship to the study drug, the interventions required to treat it, and the outcome.

Information about common side effects already known about the investigational drug can be found in the Investigator Brochure (IB) or will be communicated between IB updates in the form of Investigator Notifications. This information will be included in the patient informed consent and should be discussed with the patient during the study as needed.

## 7.2 Serious adverse event reporting

To ensure subject safety, every SAE, regardless of suspected causality, occurring after the subject has provided informed consent and until 30 days after the subject has stopped study participation (defined as time of last dose of study drug taken or last visit whichever is later) must be reported to Novartis within 24 hours of learning of its occurrence.

Any SAEs experienced after this 30-day period should only be reported to Novartis if the investigator suspects a causal relationship to the study drug. Recurrent episodes, complications, or progression of the initial SAE must be reported as follow-up to the original episode, regardless of when the event occurs. This report must be submitted within 24 hours of the investigator receiving the follow-up information. An SAE that is considered completely unrelated to a previously reported one should be reported separately as a new event.

Information about all SAEs is collected and recorded on the Serious Adverse Event Report Form. The investigator must assess the relationship of any SAE to study drug, complete the SAE Report Form in English, and send the completed, signed form by fax within 24 hours to the local Novartis Drug Safety and Epidemiology Department. The telephone and telecopy number of the contact persons in the local department of Clinical Safety and Epidemiology, specific to the site, are listed in the investigator folder provided to each site. The original copy of the SAE Report Form and the fax confirmation sheet must be kept with the case report form documentation at the study site.

Follow-up information is sent to the same person to whom the original SAE Report Form was sent, using a new SAE Report Form stating that this is a follow-up to the previously reported SAE and giving the date of the original report. The follow-up information should describe whether the event has resolved or continues, if and how it was treated, whether the drug was broken or not, and whether the subject continued or withdrew from study participation.

If the SAE is not previously documented in the Investigator's Brochure or Package Insert (new occurrence) and is thought to be related to the Novartis study drug, a Drug Safety and Epidemiology Department associate may urgently require further information from the investigator for Health Authority reporting. Novartis may need to issue an Investigator Notification (IN) to inform all investigators involved in any study with the same drug that this SAE has been reported. Suspected Unexpected Serious Adverse Reactions (SUSARs) will be collected and reported to the competent authorities and relevant ethics committees in accordance with Directive 2001/20/EC or as per national regulatory requirements in participating countries.

## 7.3 Pregnancies

To ensure subject safety, each pregnancy in a subject on study drug must be reported to Novartis within 24 hours of learning of its occurrence. The pregnancy should be followed up to determine outcome, including spontaneous or voluntary termination, details of the birth, and the presence or absence of any birth defects, congenital abnormalities, or maternal and/or newborn complications.

Pregnancy should be recorded on a Clinical Trial Pregnancy Form and reported by the investigator to the local Novartis Drug Safety and Epidemiology Department. Pregnancy follow-up should be recorded on the same form and should include an assessment of the possible

relationship to the Novartis study drug of any pregnancy outcome. Any SAE experienced during pregnancy must be reported on the SAE Report Form.

Pregnancy outcomes are not required for the female partners of the male patients who took study drug in this study.

## **7.4 Data Monitoring Committee**

Not applicable.

# **8 Data review and database management**

## **8.1 Site monitoring**

Before study initiation, at a site initiation visit or at an investigator's meeting, a Novartis representative will review the protocol and eCRFs with the investigators and their staff. During the study, the field monitor will visit the site regularly to check the completeness of patient records, the accuracy of entries on the eCRFs, the adherence to the protocol and to Good Clinical Practice, the progress of enrollment, and to ensure that study drug is being stored, dispensed, and accounted for according to specifications. Key study personnel must be available to assist the field monitor during these visits.

The investigator must maintain source documents for each subject in the study, consisting of case and visit notes (hospital or clinic medical records) containing demographic and medical information, laboratory data, electrocardiograms, and the results of any other tests or assessments. All information on eCRFs must be accessible to these source documents in the subject's file. The investigator must also keep the original informed consent form signed by the subject (a signed copy is given to the subject).

The investigator must give the monitor access to all relevant source documents to confirm their consistency with the eCRF entries. Novartis monitoring standards require full verification for the presence of informed consent, adherence to the inclusion/exclusion criteria, documentation of SAEs, and the recording of data that will be used for all primary and safety variables. Additional checks of the consistency of the source data with the eCRFs are performed according to the study-specific monitoring plan. No information in source documents about the identity of the patients will be disclosed.

## **8.2 Data collection**

Designated investigator staff will enter the data required by the protocol into the Electronic Case Report Forms using fully validated software that conforms to 21 CFR Part 11 requirements. Designated investigator site staff will not be given access to the EDC system until they have been trained. Automatic validation programs check for data discrepancies and, by generating appropriate error messages, allow the data to be confirmed or corrected before transfer of the data to the CRO working on behalf of Novartis. The Investigator must certify that the data entered into the Electronic Case Report Forms are complete and accurate. After database lock, the investigator will receive a CD-ROM or paper copies of the subject data for archiving at the investigational site.

### **8.3 Database management and quality control**

The data management vendor and Novartis staff will review the data entered into the eCRFs by investigational staff for completeness and accuracy and instruct the site personnel to make any required corrections or additions. Obviously errors are corrected by Clinical data manager. Queries are sent to the investigational site using an electronic query. Designated investigator site staff is required to respond to the query and confirm or correct the data. If the electronic query system is not used, a paper Data Query Form will be faxed to the site. Site personnel will complete and sign the faxed copy and fax it back to Novartis staff who will make the correction to the database. The signed copy of the Data Query Form is kept at the investigator site.

Concomitant medications entered into the database will be coded using the WHO Drug Reference List, which employs the Anatomical Therapeutic Chemical classification system.

Medical history/medical conditions and adverse events will be coded using the Medical dictionary for regulatory activities (MedDRA) terminology.

Throughout the study, the occurrence of any protocol deviations will be determined. After these actions have been completed and the database has been declared to be complete and accurate, it will be locked and made available for data analysis. Any changes to the database after that time can only be made by joint written agreement between the Global Head of Clinical Information Sciences and the Clinical Franchise Head.

Corporate Confidential Information

## **9 Data analysis**

### **9.1 Analysis sets**

All patients who received study drug will be included in the safety analysis set.

All patients in the safety analysis set with evaluable PK data and with no major protocol deviations that have an impact on PK data will be included in the PK analysis set.

Corporate Confidential Information

## **9.2 Subject demographics and other baseline characteristics**

All data for background and demographic variables will be listed by treatment group and patients. For these parameters summary statistics will be provided by treatment group (i.e., each LFG316 treatment group). Corporate Confidential Information

Relevant medical history, current medical conditions, results of laboratory screens, drug tests and any other relevant information will be listed by treatment group and patients.

## **9.3 Treatments (study drug, rescue medication, other concomitant therapies, compliance)**

Study drug administration (including date, time of injection) will be listed by treatment and patients.

## **9.4 Analysis of the primary variable(s)**

The primary objective of the study is to assess the effect of IVT LFG316 on Day 85 response rate in patients with active NIU requiring intensification of systemic immunosuppressive therapy. The analysis of safety data is described in [Section 9.5.2](#). Additional analysis of ocular safety is described in [Section 9.5.8](#).

### **9.4.1 Response rate**

The primary endpoint is the response rate (proportion of patients that respond in the study eye) and the remission (complete response) rate at Day 85. The analysis of response rate at Day 85 will be carried out on the PD analysis set. Patients will be analyzed as treated. The 90% confidence intervals for the proportion of responders in the LFG316 Corporate Confidential Information

as well as the 90% confidence interval for the difference in response rates will be reported. The response rates at other time points (e.g., at Days 15, 29, 57) will be analyzed similarly.

Corporate Confidential Information

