## Corporate Confidential Information

### **5 Statistical methods: Analysis sets**

Patients will be analyzed and reported based on the treatment received.

All patients who received study drug Corporate Confidential Information will be included in the safety analysis set.

All patients in the safety analysis set with evaluable PK data and with no major protocol deviations that have an impact on PK data will be included in the PK analysis set.

All patients in the safety analysis set with evaluable PD data (Total C5) with no major protocol deviations that have an impact on PD data will be included in the PD analysis set.

All patients in the safety analysis set who receive any study treatment Corporate Confidential Information with evaluable efficacy data for at least one efficacy endpoint/s (ocular assessments) and with no major protocol deviations that have an impact on efficacy data will be included in the first efficacy (Efficacy 1) analysis set. For the Efficacy 1 analysis set, any patient who discontinues after receiving at least one dose of study drug will be included up to the time of discontinuation or until the time they received rescue medication.

All patients in the safety analysis set who receive any study treatment Corporate Confidential Information with evaluable primary efficacy endpoint (response rate and remission rate on Day 85) and with no major protocol deviations that have an impact on the primary efficacy endpoint will be included in the second efficacy (Efficacy 2) analysis set.

Corporate Confidential Information

Corporate Confidential Information

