## **7 Statistical methods for Efficacy and Pharmacodynamic (PD) parameters**

### **7.1 Primary endpoint**

The primary endpoints are the response rate (proportion of patients that respond in the study eye) and the remission rate (complete response) at Day 85.

A response will be defined by any one of the following criteria in the study eye:

- An improvement of 2 or more steps in vitreous haze, relative to baseline. For the purpose of “step” calculation, 0.5 shall count as one of the increments. Thus, improvement from a score of 2 to 0.5 or from 1 to 0 would constitute a 2-step improvement or,
- An improvement of 10 or more letters in visual acuity, relative to baseline or,
- An improvement of 2 or more steps in anterior chamber cells, relative to baseline
- Resolution of chorioretinal lesions as determined by the investigator

Remission (complete response) will be defined as

- any patient who has a vitreous haze score of 0 or 0.5 in the study eye, who has an anterior chamber cell score of 0 and no chorioretinal lesions in the study eye and is off all immune modulatory therapy (systemic, corticosteroids and topical), without any worsening of uveitis during the trial.

The analysis of response rate and remission rate at Day 85 will be carried out on the efficacy analysis sets (Efficacy 1 and Efficacy 2), with the analysis on the Efficacy 1 analysis set being of primary interest.

The baseline value will be defined as Day 1 pre-dose value, or the screening values if the Day 1 pre-dose value does not exist.

The response rates and the 90% exact (Clopper-Pearson) confidence intervals in the LFG316 group Corporate Confidential Information will be reported. Corporate Confidential Information

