### **7.2.2 PD endpoint: Total C5 Concentrations**

Total C5 will be analyzed on the PD analysis set. Summary statistics of total C5 concentrations will be provided by treatment and visit/time. Total C5 concentrations will be expressed as  $\mu\text{g/mL}$ . All concentrations below the limit of quantification (LLOQ) or missing data will be labeled as such in the concentration data listings. Concentrations below the LLOQ will be treated as zero in summary statistics for concentration data only.

Arithmetic mean (SD) concentration-time plots as well as overlaying individual concentration-time profiles will be provided.

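### Protocol and SAP name different primary analysis sets, and the SAP's Efficacy 1 rules can remove rescued patients from the Day 85 denominator

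*Protocol*

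**What the plan says.** On the analysis set:

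- Protocol 9.4.1, on the primary endpoint: "The analysis of response rate at Day 85 will be carried out on the PD analysis set".
- SAP 7.1 uses two efficacy sets for the same endpoint, "with the analysis on the Efficacy 1 analysis set being of primary interest".
- SAP Section 5 builds the PD set from "All patients in the safety analysis set with evaluable PD data (Total C5) with no major protocol deviations that have an impact on PD data". SAP 7.2.2 then gives it a single visible use: "Total C5 will be analyzed on the PD analysis set".
- The protocol's own definition of the PD set cannot be read. Section 9.1 shows the safety set ("All patients who received study drug will be included in the safety analysis set") and the PK set, and the text after that is blacked out.

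On patients who stop or are rescued:

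- Efficacy 1 takes treated patients "with evaluable efficacy data for at least one efficacy endpoint/s (ocular assessments) and with no major protocol deviations that have an impact on efficacy data". Those who discontinue after a dose "will be included up to the time of discontinuation or until the time they received rescue medication" (SAP Section 5).
- The missing-data rules in SAP 7.1 class response as missing when every responder parameter is missing. A patient is a non-responder only if at least one parameter is available and no criterion is met.
- SAP 7.4 imputes nothing and assumes data are missing at random.
- Protocol 5.5.6.1 stops study drug and starts conventional therapy for vision loss attributed to uveitis, for clearly worse inflammation, or for a fellow-eye or bilateral flare that needs systemic treatment. Rescued patients are asked to keep attending the scheduled visits.

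**The concern.** The two documents give different rules for who enters the primary proportion. That needs reconciling whatever the protocol's PD set was meant to be, because one label now stands for a set that the SAP reserves for a serum measurement.

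The larger issue is what the SAP's chosen set does. Rescue of the study eye for vision loss or worse inflammation is evidence that treatment has failed. If data stop at rescue and the resulting gap is classed as missing, the failures leave the denominator while the responders stay. The missing-at-random assumption does not repair this: a raw proportion among patients with data is not adjusted for why the others are absent. In an arm of 16, a few such patients move the response rate and its interval a long way, and those are the quantities that will be read against the 60% benchmark.

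**Working it through.** **The plan's own figures.** The sample-size paragraph of the protocol synopsis gives n = 16 and a null rate of 0.60, tested one-sided. With X ~ Binomial(16, p), P(X ≥ 12) is 0.1666 at p = 0.60, and 0.4499, 0.7982 and 0.9209 at p = 0.70, 0.80 and 0.85. These match the stated 17% and 45%, 80%, 92%. (The printed threshold, read as at least 11, gives 0.3288 and 0.6598, 0.9183, 0.9765. The stated figures therefore fit more than 11 of 16, which is a separate matter.) They assume that all 16 patients are in the denominator.

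**A rescued patient followed through the SAP.**

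1. Rescue stops study drug (Protocol 5.5.6.1), so the patient has discontinued after dosing.
2. Efficacy 1 data end at that time. The Day 85 examination, which the protocol still asks for, falls after the cut-off.
3. With every Day 85 responder parameter unavailable, response is missing, not a failure (SAP 7.1).
4. Nothing is imputed (SAP 7.4), and no visible rule turns rescue into non-response.
5. On this reading the patient is absent from the Day 85 proportion.

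Efficacy 2 may not bring these patients back. It requires an evaluable Day 85 primary endpoint and excludes users of prohibited medication (code M01, SAP Table 5-2). Protocol Table 5-1 prohibits new systemic steroids or immunomodulatory therapy in the LFG316 arm, and the SAP does not say whether rescue is coded M01.

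Remission behaves differently. It requires no worsening of uveitis during the trial, so a patient rescued for worsening already fails one criterion and would be a non-remission under SAP 7.1. The two primary endpoints could then have different denominators.

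**Size.** Let n be the dosed LFG316 patients, x the responders, and k the non-responders rescued before Day 85. The rate is x/n if all are kept and x/(n − k) if the k are removed, so it is inflated by the factor n/(n − k). The 90% Clopper-Pearson limits (the method in SAP 7.1), for denominator m, are the 0.05 quantile of Beta(x, m − x + 1) and the 0.95 quantile of Beta(x + 1, m − x). The documents give no rescue rate, so k = 0 to 4 and x = 10 or 12 are assumptions.

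| k removed | x = 10: rate (90% CI) | x = 12: rate (90% CI) |
|---|---|---|
| 0 | 10/16 = 62.5% (0.391-0.822) | 12/16 = 75.0% (0.516-0.910) |
| 1 | 10/15 = 66.7% (0.423-0.858) | 12/15 = 80.0% (0.560-0.943) |
| 2 | 10/14 = 71.4% (0.460-0.896) | 12/14 = 85.7% (0.615-0.974) |
| 3 | 10/13 = 76.9% (0.505-0.934) | 12/13 = 92.3% (0.684-0.996) |
| 4 | 10/12 = 83.3% (0.562-0.970) | 12/12 = 100% (0.779-1.000) |

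With x = 10 and k = 3 the factor is 16/13 = 1.23, a shift of 76.9 − 62.5 = 14.4 percentage points. The exact one-sided p-value against 0.60 moves from 0.527 to 0.169.

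**The case against.** A reader might infer that the protocol makes the eye endpoint depend on a serum assay, so that a patient with a valid Day 85 examination but no C5 result is dropped. The documents do not support that. The C5 criterion is visible only in the SAP. The protocol uses PD loosely: Section 6.4 puts ocular measures and total C5 under one efficacy and pharmacodynamic heading, and 9.5.1 calls the secondary endpoints PD endpoints. Its PD set may simply have been the efficacy set, which the SAP later split. C5 is also sampled at nearly every visit from Day 1, so a dosed patient with none may be rare. Nor does the illustration rest on C5: its whole shift comes from the cut-off at rescue.

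Other limits also stand. The sets may turn out to hold the same patients. The choice of set cannot be said to decide the trial, because SAP 7.1 says that no decision should rest on the p-value. A reason for the change of set, or a rule for rescued patients, may be in blacked-out text, so the change cannot be called unexplained. The SAP also does not spell out that the cut-off makes Day 85 response missing; that follows from reading three rules together.

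Finally, the cut-off has a purpose: it stops improvement on conventional therapy being credited to LFG316. That is a good reason not to use post-rescue data as response. It is not a reason to remove the patient from the denominator.

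**Conclusion.** The concern holds in this form: the documents name different sets for the primary analysis, and the visible rules for the SAP's set allow patients rescued for worsening uveitis to leave the Day 85 denominator. The bias is upward. Under the assumption of 3 rescued non-responders among 16 dosed patients, with 10 responders, it takes the reported rate from 62.5% to 76.9%. It is zero if no one is rescued or discontinues before Day 85.

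The direction assumes that the removed patients are mainly failures. Patients rescued solely for the fellow eye may be doing well in the study eye, so their removal is not the same bias, and they need a rule of their own. Dependence of the primary endpoint on C5 remains a possible reading and no more.

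**What to change.** - Name one primary set in Protocol 9.4.1 and in SAP Sections 5 and 7.1: all randomised patients who received at least one dose of study treatment, whether or not C5 is evaluable. Record the reason for the change from the PD set.
- Keep patients rescued or discontinued before Day 85 in the denominator, and count them as non-responders in the primary analysis.
- State how a patient replaced after rescue solely for the fellow eye, and the replacement, are counted. Protocol Section 4 and 5.5.6.2 provide for such replacement, so both could otherwise enter the same denominator. Show a sensitivity analysis for them.
- Reserve the PD set for total C5. Keep the current Efficacy 1 and Efficacy 2 analyses as sensitivity analyses, and say whether rescue is coded M01.

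The cost is wording and derivation rules, with no new visits or data. The reported rate may be less favourable, and counting fellow-eye rescues as failures is conservative, which the sensitivity analysis would show.
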